#### **10.4.4 Pharmacokinetics**

Plasma concentrations of AC176 will be used to calculate the PK parameters. These parameters will be listed by individual patient and summarized by descriptive statistics (means, medians, ranges, standard deviations and coefficients of variation as appropriate) by cohort.

Further details on the PK analyses will be documented in the Statistical Analysis Plan (SAP).

#### **10.5 Analysis Time Points**

##### **10.5.1 Final Analysis**

The final analysis of the study will occur after the last visit of the last patient.

##### **10.5.2 Interim Analysis**

No formal interim analysis is planned.

##### **10.5.3 Safety Review**

An SRC will be established by Development Innovations for this study with members as described in the SRC section (Section [5.1.6](#)).

Once there are evaluable patients at a dose level, the SRC will review and assess all available safety data and any other relevant data from the cohort to make a decision on how the study should proceed. Any dose interruptions and reductions will be taken into account. When available, emerging PK data for plasma exposure will be evaluated to inform the dose-escalation or dosing regimen decisions on at least a prior dose level lagging basis.

The decision may be to:

- Proceed with dose-escalation
- Expand the cohort
- De-escalate the dose to a previous lower dose level or to an intermediate lower dose level
- Stop the dose-escalation part of the study

When there are other patients that are ongoing at the time of this review, the SRC may decide to defer their decision until these further patients become evaluable.

Any patient started on treatment in error, as he failed to comply with all of the eligibility criteria but meets the criteria of an evaluable patient, will be reviewed on a case-by-case basis by the SRC to determine if the patient should be included or excluded in the evaluation of dose-escalation.

The decisions and decision-making of the SRC on the next dose level will be documented and provided to the Investigators prior to dosing any new patients.

The SRC will be consulted throughout the study on issues related to study safety. The timing, frequency, or need for safety evaluations may be revised, in consultation with the SRC, in response to emerging data.

*CONFIDENTIAL*

Study Drug: AC176

Sponsor/Development Innovations Study Number: AC176-001/GU 207

Final Protocol: 10 July 2023 Version 4.0

## **11. SAFETY REPORTING AND ANALYSES**

Safety assessments will consist of monitoring and recording protocol-defined AEs and SAEs, and measurement of protocol-specified hematology, clinical chemistry, and urinalysis variables, measurement of protocol-specified vital signs, and other protocol-specified tests that are deemed critical to the safety evaluation of the study drug.

The Principal Investigator is responsible for recognizing SAEs and reporting them to the Development Innovations Safety Department (see Section 11.1.5), and the Development Innovations Safety Department in turn notifies the Sponsor (see Section 11.4). It is the Sponsor's responsibility to report relevant SAEs to the applicable local, national, or international regulatory bodies. In addition, Investigators must report SAEs and follow-up information to their responsible IRBs according to the policies of each IRB.

The Principal Investigator is also responsible for ensuring that every staff member involved in the study is familiar with the content of this section.

### **11.1 Definitions**

#### **11.1.1 Adverse Events**

Adverse event means any untoward medical occurrence associated with the use of a drug in humans, whether or not considered drug-related. An AE can be any unfavorable and unintended sign (e.g., an abnormal laboratory finding), symptom, or disease temporarily associated with the use of a drug, without any judgment about causality. An AE can arise with any use of the drug (e.g., off-label use, use in combination with another drug) and with any route of administration, formulation, or dose, including overdose.

#### **11.1.2 Serious Adverse Event**

An AE or a suspected adverse reaction (SAR) is considered “serious” if it results in any of the following outcomes:

- Death
- A life-threatening AE
- Inpatient hospitalization of at least 24 hours or prolongation of existing hospitalization
- A persistent or significant incapacity or substantial disruption of the ability to conduct normal life functions
- A congenital anomaly/birth defect

Important medical events that may not result in death, be life-threatening, or require hospitalization may be considered serious when, based upon appropriate medical judgment, they may jeopardize the patient and may require medical or surgical intervention to prevent one of the outcomes listed in this definition. Examples of such medical events include allergic bronchospasm requiring intensive treatment in an emergency room or at home, blood dyscrasias or convulsions that do not result in hospitalization, or development of drug dependency or drug abuse.

It is important to distinguish between “serious” and “severe” AEs, as the terms are not synonymous. Severity is a measure of intensity; however, an AE of severe intensity need not necessarily be considered “serious.” Seriousness serves as the guide for defining regulatory

*CONFIDENTIAL*

reporting obligations and is based on patient/event outcome or action usually associated with events that pose a threat to a patient's life or vital functions. For example, nausea that persists for several hours may be considered "severe" nausea but may not be considered an SAE. On the other hand, a stroke that results in only a limited degree of disability may be considered only a mild stroke but would be considered an SAE. "Severity" and "seriousness" should be independently assessed when recording AEs on the eCRF screen and SAEs on the SAE Report Form.

### **11.1.3 Adverse Reaction**

An adverse reaction means any AE caused by a drug. Adverse reactions are a subset of all SARs where there is a reason to conclude that the drug caused the event.

### **11.1.4 Suspected Adverse Reaction**

Suspected adverse reaction (SAR) means any AE for which there is a reasonable possibility that the drug caused the AE. "Reasonable possibility" means that there is evidence to suggest a causal relationship between the drug and the AE. An SAR implies a lesser degree of certainty about causality than adverse reaction, which means any AE caused by a drug.

### **11.1.5 Recording and Reporting of Adverse Events**

#### **Recording of Adverse Events**

All AEs of any patient during the course of the research study will be recorded in the eCRF, and the Investigator will give his or her opinion as to the relationship of the AE to the study drug treatment (i.e., whether the event is related or unrelated to study drug administration).

All AEs should be documented. A description of the event, including its date of onset and resolution, whether it constitutes an SAE or not, any action taken (e.g., changes to study treatment), and outcome should be provided along with the Investigator's assessment of causality (i.e., the relationship to the study treatment). For an AE to be a suspected treatment-related event, there should be at least a reasonable possibility of a causal relationship between the protocol treatment and the AE. Adverse events will be graded according to the NCI [CTCAE Version 5.0](#), and changes will be documented.

If the AE is serious, it should be reported immediately to Development Innovations Safety Department. Other untoward events occurring in the framework of a clinical study are to be recorded as AEs (i.e., AEs that occur prior to assignment of study treatment that are related to a protocol-mandated intervention, including invasive procedures such as biopsies, medication washout, or no treatment run-in).

Any clinically significant signs and symptoms, abnormal test findings, changes in physical examination, hypersensitivity, and other measurements that occur will be reported as AEs and reported on the relevant eCRF screen.

Test findings will be reported as an AE if the test result requires an adjustment in the study drug or discontinuation of treatment and/or test findings require additional testing or surgical intervention, a test result or finding is associated with accompanying symptoms, or a test result is considered to be an AE by the Investigator.

#### **Reporting Period for Adverse Events**

*CONFIDENTIAL*

Study Drug: AC176

Sponsor/Development Innovations Study Number: AC176-001/GU 207

Final Protocol: 10 July 2023 Version 4.0

All AEs regardless of seriousness or relationship to AC176 treatment (called study treatment), spanning from the signing of the ICF until 30 calendar days after discontinuation or completion of study treatment as defined by the study for that patient after his last dose of study drug, are to be recorded on the corresponding screen(s) included in the eCRF.

All AEs resulting in discontinuation from the study should be followed until resolution or stabilization. All new AEs occurring during this period must be reported and followed until resolution unless, in the opinion of the Investigator, the AE or laboratory abnormality/ies is/are not likely to improve because of the underlying disease. In this case, the Investigator must record his or her reasoning for this decision in the patient's medical record.

Thirty days after completion of protocol-specific treatment or discontinuation, only AEs, SAEs, or deaths assessed by the Investigator as treatment-related are to be reported.

#### **11.1.6 Assessment of Adverse Events**

All AEs and SAEs, whether volunteered by the patient, discovered by study personnel during questioning, or detected through physical examination, laboratory test, or other means, will be reported appropriately. Each reported AE or SAE will be described by its duration (i.e., start and end dates), regulatory seriousness criteria if applicable, suspected relationship to the study drug (see following guidance), and actions taken.

To ensure consistency of AE and SAE causality assessments, Investigators should apply the following general guideline:

**YES:** There is a plausible temporal relationship between the onset of the AE and administration of the study treatment, and the AE cannot be readily explained by the patient's clinical state, intercurrent illness, or concomitant therapies, and/or the AE follows a known pattern of response to the study drug, and/or the AE abates or resolves upon discontinuation of the study drug or dose reduction and, if applicable, reappears upon re-challenge.

**NO:** Evidence exists that the AE has an etiology other than the study drug (e.g., pre-existing medical condition, underlying disease, intercurrent illness, or concomitant medication), and/or the AE has no plausible temporal relationship to study drug administration (e.g., cancer diagnosed 2 days after first dose of study drug).

#### **11.2 Serious Adverse Event Reporting by Investigators**

Adverse events classified by the treating Investigator as "serious" require expeditious handling and reporting to the Development Innovations Safety Department in order to comply with regulatory requirements. Determination of "life-threatening" or "serious" is based on the opinion of either the Sponsor or the Investigator.

Serious AEs occurring at any time from the signing of the ICF through the 30-day follow-up period after the last study treatment must be reported as SAEs on the Development Innovations SAE Report Form and followed until resolution (with autopsy report if applicable). **The Development Innovations Safety Department must be notified of all SAEs, regardless of causality, within 24 hours of the first knowledge of the event by the treating physician or research personnel.**

To report an SAE, the SAE Report Form should be completed with the necessary information.

*CONFIDENTIAL*

Study Drug: AC176

Sponsor/Development Innovations Study Number: AC176-001/GU 207

Final Protocol: 10 July 2023 Version 4.0

The SAE Report Form should be sent to the Development Innovations Safety Department via fax or e-mail using the following contact information (during both business and non-business hours):

Sarah Cannon Development Innovations Safety Department

Safety Dept. [contact]

Safety Dept. Email: [contact]

Transmission of the SAE report should be confirmed by the site personnel submitting the report.

Follow-up information for SAEs and information on non-serious AEs that become serious should also be reported to the Development Innovations Safety Department as soon as it is available; these reports should also be submitted using the Development Innovations SAE Report Form.

The detailed SAE reporting process will be provided to the sites in the SAE reporting guidelines contained in the study reference manual.

### **11.3 Recording of Adverse Events and Serious Adverse Events**

#### **11.3.1 Diagnosis versus Signs and Symptoms**

All AEs should be recorded individually in the patient's own words (verbatim) unless, in the opinion of the Principal Investigator or designated physician, the AEs constitute components of a recognized condition, disease, or syndrome. In the latter case, the condition, disease, or syndrome should be named rather than each individual sign or symptom. If a constellation of signs and/or symptoms cannot be medically characterized as a single diagnosis or syndrome at the time of reporting, each individual event should be recorded as an AE or SAE as appropriate on the relevant form(s) (SAE Report Form and/or AE eCRF screen). If a diagnosis is subsequently established, it should be reported as follow-up information is available. If a diagnosis is determined subsequent to the reporting of the constellation of symptoms, the signs/symptoms should be updated to reflect the diagnosis.

Progression of malignancy (including fatal outcomes), if documented by use of appropriate method (e.g., as per RECIST criteria for solid tumors; see [Appendix B](#)), should not be reported as an SAE.

#### **11.3.2 Persistent or Recurrent Adverse Events**

A persistent AE is one that extends continuously, without resolution, between patient evaluation time points. Such events should be recorded only once on the SAE Report Form (if applicable) and/or the AE eCRF screen. Changes in AE grading of persistent AEs should be entered separately in the AE eCRF.

A recurrent AE is one that occurs and resolves between patient evaluation time points and subsequently recurs. All recurrent AEs should be recorded on an SAE Report Form (if applicable) and/or AE eCRF screen.

#### **11.3.3 Abnormal Laboratory Values**

If an abnormal laboratory value or vital sign is associated with clinical signs and/or symptoms, the sign or symptom should be reported as an AE or SAE, and the associated laboratory value or vital sign should be considered additional information that must be collected on the relevant eCRF screen. If the laboratory abnormality is a sign of a disease or syndrome, only the diagnosis needs to be recorded on the SAE Report Form (if applicable) and/or AE eCRF screen.

*CONFIDENTIAL*

Abnormal laboratory values will be reported as clinically significant and as an AE if the laboratory result(s) require an adjustment in the study drug or discontinuation of treatment, and/or laboratory findings require additional testing or surgical intervention, a laboratory result or finding is associated with accompanying symptoms, or a laboratory result is considered to be an AE by the Investigator.

#### **11.3.4 Deaths**

Deaths that occur during the protocol-specified AE reporting period that are attributed by the Investigator solely to progression of disease will be recorded on the “End of Study” eCRF screen. All other on-study deaths, regardless of attribution, will be recorded on an SAE Report Form and expeditiously reported to the Development Innovations Safety Department.

When recording a SAE with an outcome of death, the event or condition that caused or contributed to the fatal outcome should be recorded as the single medical concept on the SAE Report Form and Adverse Event eCRF screen. If the cause of death is unknown and cannot be ascertained at the time of reporting, record “Death NOS” (“death, cause unknown”) on the eCRF Adverse Event screen. During post-study survival follow-up, deaths attributed to progression of disease will be recorded on the “Follow-up Summary” and “Death Page” eCRF screens.

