### 5.1.3 Dose-Limiting Toxicity

Toxicity will be assessed using NCI CTCAE Version 5.0 unless otherwise specified.

A toxicity will be considered dose-limiting if it occurs during the first cycle of treatment with AC176 during the dose-escalation phase (excluding Backfill cohort patients). Dose-limiting toxicities (DLTs) will not include any toxicity related to underlying disease (including disease progression), intercurrent illness, concomitant medications, or extraneous causes. DLTs will be defined as follows:

- Any Grade 5 toxicity
- **Hematologic:**
  - Grade 4 neutrophil count decrease for >7 days; or febrile with neutrophil count decrease (ANC <1000/mm^3 with a single temperature of >38.3°C [101°F] or a sustained temperature of ≥ 38°C [100.4°F] for more than 1 hour)
  - Grade 4 platelet count decrease; or Grade 3 platelet count decrease associated with clinically significant bleeding, including any bleeding that warrants a platelet transfusion, related to drug
  - Grade 4 anemia related to drug (life-threatening consequences requiring urgent interventions)
- **Non-Hematologic:**
  - Grade 3 or 4 non-hematologic toxicity, with the **exception of**:
    - Alopecia;
    - Grade 3 nausea, vomiting, or diarrhea if well-controlled by supportive care within 72 hours;
    - Grade 3 skin rash that improves in ≤7 days, with or without supportive care;
    - Grade 3 fatigue that improves in ≤7 days, with or without supportive care;
    - Grade 3 endocrinopathies that only require treatment with hormone replacement therapy;

*CONFIDENTIAL*

Study Drug: AC176

Sponsor/Development Innovations Study Number: AC176-001/GU 207

Final Protocol: 10 July 2023 Version 4.0

- Grade 3 non-hematologic laboratory abnormalities, other than liver function tests, will not be considered a DLT unless they are associated with clinical manifestations which lead to medical intervention and/or hospitalization.
- Potential drug-induced liver injury consistent with Hy's Law (Appendix F), defined as AST and/or ALT  $>3 \times$  ULN with concurrent total bilirubin  $>2 \times$  ULN without findings of cholestasis (alkaline phosphatase [ALP]  $>2 \times$  ULN)
- Grade 3 or higher electrolyte abnormality that lasts  $>72$  hours, unless the patient has clinical symptoms, in which case all Grade 3 or higher electrolyte abnormalities regardless of duration should count as a DLT

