### On-Study Disease Assessments

- PSA results are to be collected on Day 1 of each treatment cycle
  - Continue through early rises for a minimum of 12 weeks unless there is other evidence of progression, as favorable effects on PSA may be delayed for  $\geq 12$  weeks
  - Ignore PSA rises before 12 weeks in determining PSA response

Patients with PSA progression are allowed and encouraged to continue treatment until symptomatic or radiographic progression.

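### Sections 11.3.1 and 11.3.4 apply different tests to a death from progression, so an undocumented early death can stay off the SAE form and outside the AE/SAE-based safety analysis

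*Protocol*

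**What the plan says.** Section 11.3.1 of the protocol removes from SAE reporting "Progression of malignancy (including fatal outcomes), if documented by use of appropriate method (e.g., as per RECIST criteria for solid tumors"; RECIST is given as an example of a method, not as the only one.

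Section 11.3.4 deals with "Deaths that occur during the protocol-specified AE reporting period that are attributed by the Investigator solely to progression of disease". These go on the End of Study eCRF screen. For the rest, "All other on-study deaths, regardless of attribution, will be recorded on an SAE Report Form", with expedited reporting to the safety department. No documentation of progression is asked for.

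The general rules are broader. Section 11.1.2 lists death among the outcomes that make an event serious, and Section 11.2 says the safety department "must be notified of all SAEs, regardless of causality, within 24 hours of the first knowledge of the event". The AE window in Section 11.1.5, "spanning from the signing of the ICF until 30 calendar days after discontinuation or completion of study treatment", includes Cycle 1.

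For dose escalation, Section 5.1.3 counts any Grade 5 toxicity in Cycle 1 as a DLT, but DLTs "will not include any toxicity related to underlying disease (including disease progression"). That exclusion has no documentation test either.

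**The concern.** Two current sections set different conditions for the same exemption, and the looser one is in the section headed Deaths, where site staff will look. Two sites could report identical deaths differently, and neither would be in breach of the section it followed.

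The gap matters most early in treatment, when toxicity and rapid progression are hardest to tell apart and imaging evidence is least likely to exist. Section 10.4.3 builds the safety analysis on reported treatment-emergent AEs and SAEs. A death recorded only on the End of Study screen does not enter those summaries, and without an SAE form it does not reach the sponsor's own assessment of relatedness by the usual route. In a first-in-human 3+3 study, one death more or less can change the action that Table 4 prescribes.

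**Working it through.** The protocol states no figure on this point, so the check is a comparison of passages, a timing check and a labelled illustration.

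**1. The two tests side by side**

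| Death in the AE window | Under 11.3.1 | Under 11.3.4 |
|---|---|---|
| Progression documented, sole attributed cause | Exempt | Exempt |
| Progression not documented, sole attributed cause | Reportable | Exempt |
| Mixed or other cause | Reportable unless it is documented progression | Reportable |

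The conflict that loses safety information is in the second row.

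**2. Timing of scheduled evidence**

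- 28-day cycles (Table 2, footnotes n and o): first scan at 8 weeks ±5 days, so 56 − 5 = day 51 to 56 + 5 = day 61. Cycle 1 ends on day 28.
- 21-day cycles (Table 16): first scan at 6 weeks ±5 days, so 42 − 5 = day 37 to 42 + 5 = day 47. Cycle 1 ends on day 21.
- PSA is drawn on Day 1 of each cycle, so the first scheduled post-baseline value comes at Cycle 2. Appendix C then says of PSA: "Continue through early rises for a minimum of 12 weeks unless there is other evidence of progression".
- Appendix C also defines symptomatic progression, which includes ECOG deterioration to Grade 3 or higher. ECOG is scheduled on Cycle 1 Day 15.

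A Cycle 1 death will therefore usually have no scheduled on-study scan, but progression can still be recorded on symptomatic criteria.

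**3. Route out of the DLT count**

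This step belongs to Section 5.1.3. If a Cycle 1 death is attributed to progression, the exclusion applies. A patient without a DLT who was not observed for a full cycle fails the minimum safety requirement and is not evaluable; the section provides for replacement. In counts:

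- One DLT in 3 becomes 0 of 2 evaluable. A third evaluable patient is needed, and if he has no DLT the action is to escalate instead of adding three patients.
- Two DLTs in 6 becomes 1 of 5 evaluable. If the sixth has no DLT the action is to escalate instead of declaring the MTD exceeded.

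**4. Illustration (inputs assumed, not in the documents)**

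Let p be the true Cycle 1 DLT probability and m the fraction of DLTs that are deaths put down to progression and replaced. The DLT rate among evaluable patients is r = p(1 − m)/(1 − pm). Under Table 4, escalation follows 0 of 3, or 1 of 3 then 0 of 3:

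P(escalate) = (1 − r)³ + 3r(1 − r)² × (1 − r)³

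With p = 0.33:

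- m = 0: r = 0.330, P = 0.434
- m = 0.10: r = 0.297/0.967 = 0.307, P = 0.480
- m = 0.20: r = 0.264/0.934 = 0.283, P = 0.530

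At p = 0.20, m = 0.10 moves P from 0.709 to 0.744. At p = 0.50 it moves P from 0.172 to 0.203.

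**The case against.** The best defence is that the sections should be read together. Section 11.3.1 expressly covers fatal outcomes, so its documentation condition already applies to deaths. On that view 11.3.4 only says which form to use and adds a further restriction, that progression be the sole cause. This is a reasonable reading, but 11.3.4 neither refers to 11.3.1 nor repeats the condition. It sends only the remaining deaths to the SAE form, so its own wording exempts the undocumented case.

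There are real safeguards. Mixed attributions still go on an SAE form. A death of unascertainable cause has its own entry on the AE screen. Section 11.1.6 asks for evidence of another etiology, or an implausible time course, before an event is called unrelated. Preceding AEs are recorded whatever their cause, although Section 11.3.7 tells sites not to report symptoms of metastasis. The Safety Review Committee looks at all the safety data it has (Section 10.5.3). The death remains on the End of Study screen and meets the PFS and rPFS event definitions, though those analyses use the Efficacy Evaluable Set, which requires an adequate post-baseline response assessment. These points narrow the consequence; they do not remove the mismatch.

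Three stronger readings are tempting and are not supported:

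- A reader might infer that nothing scheduled in Cycle 1 can document progression. Symptomatic progression under Appendix C can be recorded then.
- A reader might infer that 11.3.4 itself removes toxic deaths from the DLT count. DLT status is set by 5.1.3, which does not depend on the SAE form.
- A reader might count the reattributed patient as an evaluable non-DLT, turning 1 of 3 straight into 0 of 3 and giving a larger rise in escalation probability. The evaluability rule prevents that.

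**Conclusion.** The inconsistency is real and should be corrected. Followed as written, 11.3.4 lets an undocumented death attributed solely to progression bypass the SAE form and 24-hour notification and fall outside the AE/SAE-based safety analysis. The documents do not support saying that the death is lost from the trial's data.

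The effect on dose escalation is a separate, related weakness in 5.1.3. Its illustrated size is about 5 percentage points (0.480 − 0.434) at 10% misattribution and about 10 points (0.530 − 0.434) at 20%, for a true DLT rate of 0.33 with replacement. The DLT rate and both misattribution fractions are assumptions, and the documents do not indicate how often such deaths would occur. The conclusion about 11.3.1 and 11.3.4 needs none of these figures.

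**What to change.** Reconcile the three passages:

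1. In 11.3.4, restrict the End of Study-only route to deaths for which progression is both the sole attributed cause and documented as 11.3.1 requires, by Appendix B imaging or recorded Appendix C criteria. Every other death in the AE reporting period goes on the SAE Report Form within 24 hours, whatever the attribution.
2. In 5.1.3, state that the Safety Review Committee reviews any Cycle 1 death in dose escalation that is attributed to progression before it is excluded from the DLT count.

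The first change applies a condition the protocol already states. The second is a modest addition to a committee review that already takes place after each dose level. The cost is a sentence in each section at the next amendment and a small number of additional SAE forms; no assessment or visit is added.
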